4.0 OVERVIEW OF STUDY DESIGN/INTERVENTION

4.1 Design

This is a therapeutic Phase III prospective randomized non-inferiority study investigating the efficacy and safety of post-operative single-fraction or high-dose hypofractionated SRS. Diagnostic and eligibility decisions for patients entering the study will involve the RSA and ultimately will be made by the consenting professionals.

Eligible patients will have undergone surgery for spinal decompression and stabilization in order to treat spinal metastases and demonstrate adequate separation between tumor and the spinal cord on post-operative CT myelogram or MRI perfusion. Contrast used for the CT myelogram will not affect renal function and will be performed regardless of the participant's renal function. The CT myelogram or MRI perfusion will be performed at all participating sites. CT myelogram will be used for treatment planning, since spinal instrumentation generates artifact in MR imaging which may complicate spinal cord contouring. For instances in which the CT myelogram cannot be tolerated by the patient, MRI with perfusion will be an acceptable alternative for treatment planning. However, post-operative MR imaging provides adequate resolution in order to reliably diagnose tumor recurrence and will be used to monitor patients for recurrence, unless patients are unable to undergo MR imaging.

Patients who are candidates for either single-fraction or high-dose hypofractionated SRS will be recruited into the study and randomized in a 1:1 fashion to one of the two treatment arms. An Acute Toxicity Assessment (see Appendix E) will be performed via phone or clinic visit within 4 weeks (\pm 10 days) after the completion of SRS. Patients will have the option to complete the MD Anderson Symptom Inventory – Spine Tumor Module (MDASI) and the Brief Pain Inventory (BPI) at the time of recruitment and at 3, 6, 9, 12, 18 and 24 months (\pm 8 weeks) after their treatment during follow-up care. At these same time points, the study investigators will complete the Spine Clinic Assessment form (see Appendix F). Follow-up MRI imaging will also be obtained at the same time points, including axial and sagittal T1, T2, STIR and gadolinium-enhanced T1 sequences. For those patients that are not candidates for

MRI, CT imaging will be performed. Patients will be monitored for development of radiation- and surgery-related toxicity or complications. Imaging will be reviewed for evidence of local tumor progression.

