7.0 RECRUITMENT PLAN

Due note is taken of the NIH policy of inclusion of women and minorities in research protocols. Patients will not be excluded from the protocol based on gender, race or age. The study population will be representative of the range of patients undergoing post-operative SRS at the participating sites.

Potential subjects will be identified by a member of the patient's treatment team, the research team and/or the protocol investigators at MSKCC, MGH, JHU, or Stanford. All subjects for this study will be recruited from a pool of patients of the investigators. Subjects who appear to be eligible will be presented with the opportunity to participate. The study will be posted on the clinicaltrials.gov website. Furthermore, the trial will be posted on the MSKCC website under clinical trials.

Patients will be approached and consented anytime between the pre-operative discussion about surgery and the start of SRS treatment planning. Once the post-operative CT myelogram or MRI perfusion demonstrates separation of tumor and the spinal cord and all of the inclusion criteria are met, the patient will be randomized before the start of radiation treatment planning to receive either single-fraction or hypofractionated SRS within 8 weeks of surgery. The recruiting physicians will be familiar with the patient's medical history and health status at the time of recruitment since they will be directly involved in the post-operative radiation planning and will not require a waiver of authorization. Screening for the eligibility will not require collection of any additional patient information since all of the information required to determine patient eligibility will be required in order to appropriately plan the post-operative SRS.

Patients will not be recruited outside of the post-operative treatment pathway and no advertisement or patient compensation will take place.

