8.0 PRETREATMENT EVALUATION

Pretreatment evaluations may be performed within 8 weeks of consent, and include the following:

- 1) Complete patient history
- 2) Complete neurologic and physical exam (specifically assessment of: skin including incision site, motor/sensory function, and ambulatory status)
- 3) Pathology review confirming metastatic cancer
- 4) MDASI (optionally)

- 5) BPI (optionally)
- 6) ECOG \leq 3
- 7) Current medications
- 8) Post-operative CT myelogram or MRI perfusion
- 9) Serum pregnancy test for women of child-bearing potential

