10.0 EVALUATION DURING TREATMENT/INTERVENTION

Pre-treatment evaluations may be performed within 8 weeks of consent. After SRS, patients will be closely monitored for any evidence of toxicity, systemic illness or tumor progression. Acute toxicity assessment (see Appendix E) will occur by phone or clinic visit within 4 weeks (± 10 days) after the completion of radiotherapy. Follow-up clinic visits will take place 3 months, 6 months, 9 months, 12 months, 18 months and 24 months (± 8 weeks) after the completion of radiotherapy. At each follow-up visit, the investigators will complete the Spine Clinic Assessment form (see Appendix F). Spine MRI or CT will also be performed at the time of each follow-up, in accordance with routine standard of care.

Table 1: Pre-therapy and Follow-up Evaluations

Item	Pre-therapy (w within 8 weeks of consent)	Follow-up (3, 6, 9, 12, 18, 24 months \pm 8 weeks after the completion of SRS)
Inclusion/exclusion criteria	X	
CT myelogram or MRI perfusion	X	
Pathology diagnosis confirming metastatic disease	X	
Medical history	X	
Pregnancy test ¹	X	
Physical exam	X	X
Concomitant medications review	X	X
ECOG	X	X
Quality of Life assessments (MDASI and BPI) ²	X	X
Spine Clinic Assessment Form	X	X
MRI/CT scan ³	X	X
Adverse-event/toxicity assessment ⁴	X	X
Consent	X	

¹ For women of child-bearing potential, a urine or blood pregnancy test must be completed within 2 weeks prior to SRS.

- ² Patients will be asked to complete quality of life (MDASI and BPI) assessments at all timepoints, however this will remain optional. In instances where these questionnaires are not available in the participant's primary language, the participant will not be required to complete the questionnaire(s).
- ³ All patients are required to have MRI/CT based imaging at baseline and 3, 6, 9, 12, 18, and 24 months (\pm 8 weeks) after SRS. The imaging modality should remain constant for each patient throughout.
- ⁴ Only treatment-related adverse events will be reported. Acute toxicity assessment (see Appendix E) will occur by phone or clinic visit within 4 weeks (\pm 10 days) after the completion of radiotherapy.

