Secondary endpoint comparison of quality of life between the two cohorts will be determined through optional patient-reported responses for the MDASI - Spine Tumor Module at each follow up visit. The MDASI Spine Tumor Specific Items (questions #14-18) will be scored separately as a Spine Tumor Symptom Severity scale.

Secondary endpoint comparison of pain control will be determined through optional patient-reported responses of the BPI. Pain severity at its worst (question #5) and the average of the pain interference (average of question #9) will serve as the pain endpoints.

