Toxicity outcomes and patterns of complications are summarized and tabulated in Section 11.0. Comparisons will be made using Wilcoxon rank sum tests and proportion tests. QOL results measured by MDASI scores and pain control results measured by BPI scores will also be summarized and compared between the two arms by Wilcoxon rank sum tests. As multiple measurements will be taken and thus multiple tests will be conducted, test p-values will be adjusted by the false discovery rate method.

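### The MDASI and BPI comparisons use unadjusted Wilcoxon tests although a baseline score is collected: valid, but they give up precision on two secondary objectives

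*Combined protocol and SAP*

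**What the plan says.** **The test.** Section 14.0 states that MDASI quality-of-life results and "pain control results measured by BPI scores will also be summarized and compared between the two arms by Wilcoxon rank sum tests". It then applies a false discovery rate adjustment because many tests are expected. It names no covariate, change score, time point or longitudinal model.

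**The endpoints.** Section 12.0 says: "Pain severity at its worst (question #5) and the average of the pain interference (average of question #9) will serve as the pain endpoints". Quality of life is compared through "optional patient-reported responses for the MDASI - Spine Tumor Module at each follow up visit", with questions 14 to 18 scored as a separate spine tumor severity scale. Neither endpoint is defined as a change from baseline.

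**The baseline.** Section 4.1 offers both forms "at the time of recruitment and at 3, 6, 9, 12, 18 and 24 months" after treatment. Footnote 2 to Table 1 in Section 10.0 requests "assessments at all timepoints, however this will remain optional".

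**Its timing.** Section 7.0 says: "Patients will be approached and consented anytime between the pre-operative discussion about surgery and the start of SRS treatment planning". Section 8.0, which lists MDASI and BPI, says: "Pretreatment evaluations may be performed within 8 weeks of consent". Neither section ties the questionnaires to surgery or to randomisation.

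**The concern.** Quality of life and pain are two of the three secondary objectives in Section 2.0. Data on them will be thin. The forms are optional, and Section 3.1 cites a median survival of 7.0 to 16.5 months against visits that run to 24 months. A patient's own baseline score usually explains part of the variation in later scores. Here it is collected at no extra cost and then left out of the comparison.

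The timing of that baseline also bears on any remedy. Section 3.2 lists better pain control among the aims of surgery, so a score taken before decompression and one taken after it measure different states. If both kinds are mixed, baseline predicts later scores less well.

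**Working it through.** **The plan's own figure.** No power, standard deviation or effect size is given for MDASI or BPI, so there is no figure to reproduce for them. The only stated power, 80% with 75 patients per arm, belongs to the primary endpoint and is used here only for the sample size. It does reproduce:
- Margin hazard ratio = ln(0.75)/ln(0.85) = 1.770.
- Two years of accrual plus two years of follow-up, exponential failure at 85% per year and no deaths give 57.5 expected events.
- One-sided alpha 0.10 gives a power of Φ(√(57.5/4) × ln 1.770 − 1.282) = 81%.

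**Assumptions, none from the documents.** Correlation r = 0.3 to 0.7; true difference 0.5 SD; two-sided alpha 0.05; no false discovery rate penalty; 75 per arm, or 35 per arm to represent deaths and uncompleted forms.

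**Variance.** Adjustment multiplies the variance of a mean comparison by 1 − r². The equivalent gain in patients is 1/(1 − r²).
- r = 0.3: factor 0.91, a 9% cut, worth 1.10 times the patients.
- r = 0.5: factor 0.75, a 25% cut, worth 1.33 times.
- r = 0.7: factor 0.51, a 49% cut, worth 1.96 times.

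**Detectable difference at 80% power, 75 per arm.**
- Wilcoxon, with efficiency 3/π = 0.955: (1.960 + 0.842) × √(2/(75 × 0.955)) = 0.47 SD.
- ANCOVA: 2.802 × √(2(1 − r²)/75) = 0.44, 0.40 and 0.33 SD at r = 0.3, 0.5 and 0.7.

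**Power at 0.5 SD by the same approximation.** With 75 per arm: 85% for Wilcoxon against 89%, 94% and 99% for ANCOVA. With 35 per arm: 53% against 59%, 68% and 83%. A small part of each gain is the 0.955 factor and not the baseline score.

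**Simulation on rounded 0 to 10 scores, 3,000 runs per case, 75 per arm.** Rank ANCOVA against Wilcoxon is the like-for-like comparison.

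| r | Wilcoxon, raw score | Wilcoxon, change | ANCOVA | Rank ANCOVA |
|---|---|---|---|---|
| 0.3 | 84% | 70% | 88% | 87% |
| 0.5 | 84% | 83% | 93% | 92% |
| 0.7 | 83% | 96% | 98% | 98% |

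Change scores have variance 2(1 − r) times that of the raw score. This exceeds 1 when r is below 0.5, so they are not a safe substitute.

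**Mixed baseline timing.** Assume half the baselines are pre-operative (r = 0.2, baseline 0.8 SD higher) and half post-operative (r = 0.6). Simulated power at 75 per arm is 83% for raw Wilcoxon, 88% for ANCOVA, 87% for rank ANCOVA and 72% for change scores. With no true difference, rejection rates in this setting were 4% to 5% for all four methods. The expected variance cut, before rounding, is:
- timing ignored: 0.4²/(1 + 0.8² × 0.25) = 0.16/1.16 = 14%;
- timing in the model as a main effect: 0.4² = 16%;
- timing with separate slopes: (0.6² + 0.2²)/2 = 20%;
- all baselines post-operative: 0.6² = 36%.

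**Missing baselines.** If patients without a baseline form were dropped, the sample would shrink to 1 − m of its size, where m is the share missing. The gain is gone once (1 − m)/(1 − r²) = 1, that is m = r²: 9%, 25% or 49% at the three correlations.

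**The case against.** The strongest reply is that nothing here is an error. A rank sum test is valid under randomisation and is a standard choice for bounded 0 to 10 scores. The endpoints are optional and secondary with no promised power, and the false discovery rate is a reasonable way to handle many tests. All of that stands. It limits the point to precision, and the gain is small if r is near 0.3.

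It can also be said that the plan refers only to scores, so an unadjusted analysis of raw scores is a reading. That is true, but Section 12.0 defines the pain endpoints as scores and no section defines a change or an adjustment. Separate tests at each visit are likewise a reading; three named scales over six visits would give 18.

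The practical objections are sound and shape the fix. Dropping patients without a baseline could cancel the gain. A mixed model assumes data missing at random and implicitly averages over scores after death. A Wilcoxon test in survivors checks neither.

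Three stronger readings are tempting and not supported:
- *Mixed baseline timing damages the planned comparison.* It cannot, because that test ignores baseline. Mixing is also possible and not shown: Section 8.0 lists the forms beside an incision-site examination and post-operative imaging, which suggests that many will be completed after surgery.
- *These scales would decide between the arms if local control is comparable.* Section 14.0 gives cost and toxicity risk as its examples. Section 3.9 names quality of life as a study aim, but not as the deciding factor.
- *The planned test is biased.* Randomisation protects it.

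**Conclusion.** The point holds as a loss of precision on two optional secondary objectives, not as a flaw of validity. Adjustment would cut variance by about 9% to 49% over r = 0.3 to 0.7, relative to an unadjusted mean comparison. In the like-for-like simulation with a 0.5 SD difference and 75 per arm, power rises from about 84% to between 87% and 98%. These figures are illustrative: they rest on an assumed correlation, difference and alpha, and take no account of the false discovery rate adjustment. Baseline timing matters only for how well the adjustment works. The primary analysis is not touched.

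**What to change.** Amend Section 14.0 so that the between-arm comparison of each scale named in Section 12.0 (MDASI spine tumor severity, BPI worst pain, BPI interference) is baseline-adjusted:
- Use ANCOVA, rank ANCOVA, or a repeated-measures model with arm, visit, arm-by-visit, baseline and the stratification factors. Do not use plain change scores.
- Report the adjusted difference with its confidence interval. Keep the false discovery rate across the contrasts, and keep the Wilcoxon test as a sensitivity analysis.
- Keep patients with no baseline form in the analysis, for example by a constrained longitudinal model with baseline as an outcome, or by a missing indicator.
- State that results apply to patients alive at each visit.
- Define baseline as a questionnaire completed after surgery and before randomisation. Section 7.0 already places the post-operative imaging before randomisation, which offers a natural occasion. Otherwise, record the timing relative to surgery and include it in the model.

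**Cost.** The analysis change is wording. The baseline definition is a small protocol change that needs approval at the lead centre and the participating sites under Section 16.3.1, and some patients who completed the form before surgery may be asked to repeat it. The model brings modest assumptions, including missing at random, which the Wilcoxon sensitivity analysis does not test. No extra patients are needed.

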3.8 Quality of Life Measures: MDASI and BPI

As part of this study, we aim to assess a variety of symptoms experienced by cancer patients and to what degree these symptoms impede with daily living at baseline and at 3, 6, 9, 12, 18, and 24 months (± 8 weeks) after treatment during follow up care. In order to measure this, we will utilize the MD Anderson Symptom Inventory – Spine Tumor Module (MDASI) as an optional measure to evaluate each cohort of the study. MDASI has been validated as an instrument for use in clinical trials^{29,34,35} with Cronbach alpha reliability ranges from 0.82 to 0.94³⁴. This instrument (see Appendix A) contains 24 questions that ask patients to self-report about symptoms experienced in the last 24 hours on a scale of 0 (not present) to 10 (as bad as you can imagine). Thus, higher scores indicate more severe symptoms. Scoring of symptom severity and scoring of symptom interference will be performed as indicated in the Outcome Measure section of the MDASI User Guide (see Appendix B).

A second optional tool we will employ is the Brief Pain Inventory (BPI) to assess both the severity of pain experienced by participants and to what degree pain invades their ability to carry out daily functions at baseline and at 3, 6, 9, 12, 18, and 24 months (± 8 weeks) after treatment during follow up care. The BPI has been validated as an instrument for use in clinical trials^{29,36} with Cronbach alpha reliability ranges from 0.77 to 0.91³⁷. Patients are asked a total of 9 questions regarding their pain during in the last 24 hours (see Appendix C). Response formats include: Yes/No, scale of 0 (no pain) to 10 (pain as bad as you can imagine), illustrated region(s) of pain, pain relief as measured by 0% (no relief) - 100% (complete relief), pain interference of daily functions scale of 0 (does not interfere) to 10 (completely interferes). Higher score responses indicate more severe pain. No scoring algorithm exists, however the arithmetic mean of the four most severe items can be used as a measure of pain severity as indicated in the BPI User Guide (see Appendix D). The

arithmetic mean of the seven interference items (of question 9) can be used as a measure of pain interference³⁷.

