An intent-to-treat, stratified log rank test will be used to test whether or not the single-fraction SRS arm is inferior to the hypofractionated (3 fractions in total) SRS arm in terms of the local control rate. To set up a formal test we will use the 1-year local control rate as the surrogate of the efficacy (assuming that the two survival curves follow exponential distributions) and allow a 10% inferior margin. From a clinical standpoint, the investigators agreed that a difference of less than 10% is not regarded as significant. On this basis, we permit a 10% inferior margin. I.e., we will test $H_0: P_1 \leq (P_2 - 10\%)$ vs $H_1: P_1 > (P_2 - 10\%)$, where P_1 and P_2 denote the 1-year local control rate for the single-fraction arm and the 3-fraction arm, respectively. To approximately assess the power of the test, we estimate that the 3-fraction arm will yield a 1-year local control rate around 85% based on interim preliminary data from a multicenter Phase III trial (Protocol 10-154), and set the type I error (that is, declare single-fraction arm noninferior while it is not) rate at 0.10. When the two arms have equal efficacy, i.e., $P_1 = P_2 = 85\%$, the power (that is, declare the single-fraction arm noninferior while it is) of this noninferiority test⁴⁰ is 80% when there are 75 patients in each arm. Besides, since deaths without local failure are likely, competing risk analysis will also be used to estimate the local control rates of the two arms over time. We plan to enroll 150 patients within 2 years. If a

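### Section 14 gives the baseline MDASI and BPI scores no role in the quality-of-life and pain comparisons; adjusting for them would be a cheap gain in precision

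*Combined protocol and SAP*

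**What the plan says.** Quality of life (MDASI) and pain control (BPI) are two of the three secondary objectives in Section 2.0. Section 3.8 schedules both instruments "at baseline and at 3, 6, 9, 12, 18, and 24 months (± 8 weeks) after treatment during follow up care". Section 4.1 places the first completion at recruitment, and Section 8.0 lists both forms, as optional items, among the pretreatment evaluations. A footnote to Table 1 in Section 10.0 reads: "Patients will be asked to complete quality of life (MDASI and BPI) assessments at all timepoints, however this will remain optional".

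Section 12.0 defines the pain outcomes as scores: "Pain severity at its worst (question #5) and the average of the pain interference (average of question #9) will serve as the pain endpoints". For analysis, Section 14.0 says that MDASI and BPI results "will also be summarized and compared between the two arms by Wilcoxon rank sum tests" and that "test p-values will be adjusted by the false discovery rate method". It does not say whether the tested quantity is the follow-up score or the change from baseline, and it names no covariate.

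Section 7.0 governs when the first form can be completed: "Patients will be approached and consented anytime between the pre-operative discussion about surgery and the start of SRS treatment planning".

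**The concern.** A patient's score before radiosurgery may predict the later score on the same instrument. Where it does, an analysis that conditions on it removes that part of the between-patient variation and narrows the interval for the arm difference. A two-sample rank sum test on follow-up scores leaves the variation in, including whatever baseline difference chance has put between the arms.

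Section 14.0 argues that if local control is comparable, physicians can choose between the schedules on other grounds, and Section 3.9 names impact on quality of life as something the study is to determine. Precision on these two objectives is therefore worth having. The number of usable forms will be limited by death (Section 3.1 cites median survival of 7.0 to 16.5 months after surgery), by the optional status of the questionnaires and by the lack of some translations.

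**Working it through.** **The only power in the plan.** Section 14.0 states a power that "is 80% when there are 75 patients in each arm". This is for the noninferiority log-rank test on local control. It can be approximated: margin hazard ratio ln(0.75)/ln(0.85) = 1.770; about 57.5 expected events with exponential failure, two-year uniform accrual, two further years of follow-up and no deaths; one-sided alpha 0.10. Then Φ(√57.5/2 × ln 1.770 − 1.2816) = Φ(0.883) = 81%. That figure does not bear on MDASI or BPI, for which no power is stated.

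**Inputs for the illustration.** All are assumptions, because the documents give none of them:
- correlation ρ between baseline and follow-up score: 0.3, 0.5, 0.7
- two-sided alpha 0.05, before any false discovery rate correction
- unadjusted power 80%, which at 75 per arm corresponds to an effect of (0.842 + 1.960) × √(2/75) = 0.457 SD
- share q of patients with a baseline form: 100%, 70%, 50%

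**Step 1, complete baselines.** Adjustment multiplies the variance by 1 − ρ². Adjusted power = Φ(2.802/√(1 − ρ²) − 1.960).

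| ρ | 1 − ρ² | adjusted power |
|---|---|---|
| 0.3 | 0.91 | 83.6% |
| 0.5 | 0.75 | 89.9% |
| 0.7 | 0.51 | 97.5% |

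At ρ = 0.5, 57 patients per arm (75 × 0.75 = 56.25, rounded up) would give the 80% that 75 give unadjusted. The gain also depends on the starting power: at ρ = 0.5, 50% becomes 61.9%, 60% becomes 72.4%, and 90% becomes 96.3%.

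**Step 2, incomplete baselines.** If patients without a baseline form are kept by mean imputation plus a missing-baseline indicator, the variance factor is roughly 1 − qρ².

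| ρ | q = 0.7: factor, power | q = 0.5: factor, power |
|---|---|---|
| 0.3 | 0.937, 82.5% | 0.955, 81.8% |
| 0.5 | 0.825, 87.0% | 0.875, 85.0% |

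From 80%, the gain is then about 5 to 7 points at ρ = 0.5 and about 2 to 2.5 points at ρ = 0.3.

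**Step 3, if change scores were meant.** With equal variances at the two times, a change score has variance 2(1 − ρ) relative to the raw score.
- ρ = 0.3: factor 1.4, power falls from 80% to Φ(2.802/√1.4 − 1.960) = 66%
- ρ = 0.5: factor 1.0, power stays at 80%
- ρ = 0.7: factor 0.6, power rises to 95%, against 97.5% with adjustment

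**Step 4, check with rank methods.** A simulation with 6,000 runs per setting, complete baselines, effect 0.457 SD and ρ = 0.5 gave the following.

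| Per arm | Wilcoxon, raw | Wilcoxon, change | rank ANCOVA | ANCOVA |
|---|---|---|---|---|
| 75 | 77.0% | 77.0% | 85.9% | 88.7% |
| 40 | 49.0% | 49.4% | 60.2% | 63.4% |

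The rank method keeps most of the gain. At 40 per arm and ρ = 0.3, raw Wilcoxon gave 50.9%, change-score Wilcoxon 38.8% and rank ANCOVA 54.3%.

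**The case against.** **The unadjusted test is valid.** Under randomization the rank sum test needs no baseline adjustment. The plan sets no power or sample-size target for these endpoints, so nothing it promises is missed. This stands, and it limits the point to efficiency.

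**The plan does not exclude change scores.** Section 14.0 refers to scores without saying raw or change. Section 12.0 leans towards raw scores, but that is an inference. The ambiguity stands. It does not remove the point, because change scores gain nothing at ρ = 0.5, lose below it, and fall short of adjustment at 0.7 as well.

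**A flat 10-point loss is not supported.** A reader might infer that the plan gives up about 10 points of power. That needs ρ = 0.5, a reference power near 80%, two-sided 0.05 and a baseline form from everyone. None of these is in the documents, and the last conflicts with the optional status of the forms. Section 3.2 lists better pain control among the goals of surgery, so forms completed before surgery may predict later pain less well, which points to the lower correlations.

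**Mixed baseline timing does not distort the planned test.** Because Section 7.0 allows consent before or after decompression, a reader might infer that the unadjusted comparison carries an imbalance between pre- and post-operative baselines. It cannot: a test on follow-up scores never uses the baseline form, so the date of that form does not enter. Timing matters only once the baseline is used, and then it complicates the adjustment.

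**Bounded items suit a rank test.** MDASI and BPI items run from 0 to 10, which favours a rank method over a linear model. This stands, and rank ANCOVA respects it.

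**Conclusion.** The point holds as a cheap improvement. Baseline MDASI and BPI scores are requested, and the analysis plan gives them no stated role. The consequence is wider uncertainty on two secondary objectives. It is not bias, not an invalid test, and it does not touch the primary endpoint.

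The size is conditional. From 80% unadjusted power at two-sided 0.05, the illustrative gain is about 4, 10 or 17.5 points at ρ of 0.3, 0.5 or 0.7 with complete baselines. With 50% to 70% of baselines present it is about 2 to 2.5 points at ρ = 0.3 and 5 to 7 at ρ = 0.5. These figures rest on assumed correlations, effect size, alpha and completion rates. The smaller ones are the more cautious guide, because the forms are optional and some baselines may precede surgery.

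**What to change.** In Section 14.0, replace the rank sum test for MDASI and BPI with a baseline-adjusted comparison at each planned visit:
- Use rank ANCOVA by preference, since the items are bounded, with the same-instrument baseline score as covariate.
- Include an indicator for whether the baseline form was completed before or after surgery, because Sections 4.1 and 7.0 together allow either.
- Keep patients who have a follow-up score but no baseline form, by mean imputation of the baseline plus a missing-baseline indicator.
- Retain the false discovery rate adjustment.

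Settle this before outcomes are examined by arm, so that the choice of covariates is not open to challenge. The cost is a change of wording and slightly more analysis work, with no new visits or forms. The gain will be smaller where baseline forms are missing or predict poorly.
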